12.5 Genomic Data Sharing Plan

N/A: no whole-exome sequencing data will be generated for research purposes on this study.

12.6 NIH Human Data Sharing Plan

What data will be shared?

We will share human data generated in this research for future research as follows:

- De-identified data in an NIH-funded or approved public repository
- Identified data in BTRIS (automatic for activities in the Clinical Center)
- De-identified or identified data with approved outside collaborators under appropriate agreements

How and where will the data be shared?

Data will be shared through:

- An NIH-funded or approved public repository: clinicaltrials.gov
- BTRIS (automatic for activities in the Clinical Center)
- Approved outside collaborators under appropriate individual agreements
- Publication and/or public presentations

When will the data be shared?

- At the time of publication or shortly thereafter

12.7 Incidental/Secondary Findings Disclosure Procedure

N/A

13. HUMAN SUBJECTS PROTECTIONS

This study will be open to all individuals regardless of gender, ethnicity, or race, provided that the aforementioned inclusion and exclusion criteria are met. Patients for this study will be recruited through internal referral, our physician referral base, and through various cancer information hotlines (i.e., Clinical Studies Support Center, [name]). To date, there is no information that suggests that differences in drug metabolism or effect on tumor would be expected in one ethnic group compared to another. Efforts will be made to extend accrual to each representative population, but a balance must be struck between participant safety considerations and limitations on the number of individuals exposed to potentially ineffective treatments on the one hand and the need to explore racial/ethnic aspects of clinical research on the other hand. If differences in outcome that correlate to ethnic identity are noted, a follow-up study may be written to investigate those differences more fully.

Because p97 inhibitors are likely to have teratogenic effects, pregnant and nursing women will be excluded from this trial. Patients with unstable or serious medical conditions are excluded due to the possibility that the underlying condition may obscure the attribution of effect and adverse events with respect to CB-5339 and may limit study compliance.

This study includes patients 18 years of age and older. Because no clinical dosing or adverse event data are currently available on the use of CB-5339 in patients <18 years of age, children are excluded from this study, but may be eligible for future pediatric trials.

13.1 Evaluation of Benefits and Risks/Discomforts

There may or may not be any clinical benefit to a patient from participation in this trial. Their participation will benefit future cancer patients. Potential risks include the possible occurrence of any of a range of side effects that are listed in the consent document. The procedure for protecting against or minimizing risks will be to medically evaluate patients as described in Section 5. Although no compensation is available, any injury will be fully evaluated and treated in keeping with the benefits or care to which participants are entitled under applicable regulations.

13.2 Consent and Assent Process and Documentation

An associate or principal investigator on the trial will inform patients of the purpose, alternatives, drug administration plan, research objectives, and follow-up of this trial. The patient will be provided an IRB-approved consent for review and signature and his/her questions will be answered. After a decision is made to enroll into the study, a signature will be obtained from the patient. The original signed consent goes to Medical Records; a copy will be placed in the research record. Patients will not be consented by telephone.

All patients must have a signed informed consent form and an on-study (confirmation of eligibility) form filled out and signed by a participating investigator before entering on study.

13.3 Procedure for Protecting Against or Minimizing Any Potential Risks

All care will be taken to minimize side effects, but they can be unpredictable in nature and severity. This study may involve risks to patients, which are currently unforeseeable. All patients will be monitored for side effects from taking study medication. This research represents a greater than minimal risk to participants, but presents the prospect of direct benefit to individual subjects.

APPENDIX A: PERFORMANCE STATUS CRITERIA

ECOG Performance Status Scale		Karnofsky Performance Scale	
Grade	Descriptions	Percent	Description
0	Normal activity. Fully active, able to carry on all pre-disease performance without restriction.	100	Normal, no complaints, no evidence of disease.
		90	Able to carry on normal activity; minor signs or symptoms of disease.
1	Symptoms, but ambulatory. Restricted in physically strenuous activity, but ambulatory and able to carry out work of a light or sedentary nature (e.g., light housework, office work).	80	Normal activity with effort; some signs or symptoms of disease.
		70	Cares for self, unable to carry on normal activity or to do active work.
2	In bed <50% of the time. Ambulatory and capable of all self-care, but unable to carry out any work activities. Up and about more than 50% of waking hours.	60	Requires occasional assistance, but is able to care for most of his/her needs.
		50	Requires considerable assistance and frequent medical care.
3	In bed >50% of the time. Capable of only limited self-care, confined to bed or chair more than 50% of waking hours.	40	Disabled, requires special care and assistance.
		30	Severely disabled, hospitalization indicated. Death not imminent.
4	100% bedridden. Completely disabled. Cannot carry on any self-care. Totally confined to bed or chair.	20	Very sick, hospitalization indicated. Death not imminent.
		10	Moribund, fatal processes progressing rapidly.
5	Dead.	0	Dead.

APPENDIX B: PATIENT OPHTHALMOLOGIC QUESTIONNAIRE AND EYE EXAM

Today's date _____

Agent: CB-5339

[figure not shown]
Patient Name _____ (*initials acceptable*) Patient Study ID _____

Reason for questionnaire (screening/Cycle 1 day 1 or 2/as clinically indicated): _____

[figure not shown]
Please complete this form by placing an "X" on the line marking a place on the scale that indicates your answer to the questions about your eyes and vision.

For us to best understand the status of your eyes and vision and how they affect your quality of life, your answers must be as accurate as possible. If you wear glasses or contact lenses to improve your vision, please answer all of the following questions as though you were wearing them.

1. How would you describe your vision in your right eye, on average, over the past month?

[figure not shown]
2. How would you describe your vision in your left eye, on average, over the past month?

Blind / No vision whatsoever

Perfectly normal vision

[figure not shown]
4. How would you describe your vision in your right eye today?

Blind / No vision whatsoever

Perfectly normal vision

[figure not shown]
5. How would you describe your vision in your left eye today?

Blind / No vision whatsoever

Perfectly normal vision

[figure not shown]
6. How would you describe the way your eyes have felt on average over the past month?

At least one eye has been very painful

No discomfort in either eye

[figure not shown]
7. How would you describe the way your eyes feel today?

At least one eye is very painful

No discomfort in either eye

[figure not shown]
8. Have you noticed any visual disturbances in either eye over the past month?

Severe visual disturbances

[figure not shown]
No visual disturbances

9. Do you notice any visual disturbances in either eye today?

[figure not shown]

C1D1 or D2

[figure not shown]
10. How would you describe your vision in your right eye, on average, since you started taking study drug?

[figure not shown]
11. How would you describe your vision in your left eye, on average, since you started taking study drug?

[figure not shown]
12. How would you describe your vision in your right eye today?

13. How would you describe your vision in your left eye today?

[figure not shown]
14. How would you describe the way your eyes have felt on average since you started taking study drug?

[figure not shown]
At least one eye has been very painful

No discomfort in either eye

[figure not shown]
15. How would you describe the way your eyes feel today?

16. Have you noticed any visual disturbances in either eye since you started taking study drug?

17. Do you notice any visual disturbances in either eye today?

Severe visual disturbances

No visual disturbances

Ophthalmologic Examination will be performed at screening and as clinically indicated.

Ophthalmologic testing and biomicroscopic examinations should include assessment of the following in the order listed whenever possible.

- Best corrected visual acuity (BCVA) using Early Treatment Diabetic Retinopathy Study (ETDRS) methodology. The same methodology is to be used for the pre-study and follow-up examinations for each individual subject.
- Slit lamp examination including assessment of the lids, lashes, conjunctiva, sclera, cornea, anterior chamber, iris, lens and anterior vitreous. The slit lamp examination is repeated following dilation to better assess the lens and anterior vitreous.
- Measurement of intra-ocular pressure.
- Fundus examination. This include assessment of the vitreous, retina, disc, macula, vessels, and periphery of each eye using dilated fundoscopy.
- Spectral domain optical coherence tomography (OCT) of the macula and disc for both eyes. The same type of device is to be used for the pre-study and follow-up examinations for each individual subject.
- Standard field fundus photographs with the pupils dilated performed on each eye to aid in the evaluation of the optic nerve, vessels, macula, and periphery.
- Color vision testing

To be eligible for this research protocol, patients will be screened for pre-existing visual impairment. Patients will be excluded if they do not meet the visual acuity threshold (best corrected visual acuity of 60 ETDRS letters [Snellen equivalent of 20/60] in either eye) and the visual field threshold (substantial visual field loss in one or both eyes).

APPENDIX C: PD/PK COLLECTION WORKSHEETS

CTEP Protocol 10349 CB-5339 dose: Patient ID:	Height: Weight: BSA:	Page [name] for Sample Pick-up Lab [contact]	Research Nurse: Phone: [name]: [contact] Pager:																																																																								

PLEASE ENTER DATE, TIME, and VOLUME OF EACH VOID of URINE FOR 24 HOURS POST DRUG ADMINISTRATION; KEEP SAMPLES REFRIGERATED UNTIL PICKED UP
 
  
 Date	Time	Volume of Void	Record comments (i.e., if collection missed), and sign each time you collect a sample	
   
 Pre-Drug Administration (Sample 100)	
 
 				
 
 Administer CB-5339, Time:	
 
  
DAY 1 Start 24-hour urine collection immediately after study drug administration, keep on ice. Add 1.5% BSA to collection flask and mix well. Record volume of each void on this sheet and record total 24-hour volume at the end of the collection. At the end of 24 hours, retain 10 mL aliquot only, place on ice and discard remainder of urine.
 	
 
 Date	Time (start of 24 hr collection time)	Volume of Void	24-hour urine collection	
 
 			Volume 1	
 
 			Volume 2	
 
 			Volume 3	
 
 			Volume 4	
 
 			Volume 5	
 
 			Volume 6	
 
 			Volume 7	
 
 			Volume 8	
 
 			Volume 9	
 
 			Volume 10	
 
 Total (24-hour volume)			10 mL aliquot obtained BSA added (please check boxes) Sample #101	
 
 End 24-hour Collection Time:	
  
				Date	Time	Volume of Void	Record comments (i.e., if collection missed), and sign each time you collect a sample	Pre-Drug Administration (Sample 100)								Administer CB-5339, Time:				
DAY 1 Start 24-hour urine collection immediately after study drug administration, keep on ice. Add 1.5% BSA to collection flask and mix well. Record volume of each void on this sheet and record total 24-hour volume at the end of the collection. At the end of 24 hours, retain 10 mL aliquot only, place on ice and discard remainder of urine.
				Date	Time (start of 24 hr collection time)	Volume of Void	24-hour urine collection				Volume 1				Volume 2				Volume 3				Volume 4				Volume 5				Volume 6				Volume 7				Volume 8				Volume 9				Volume 10	Total (24-hour volume)			10 mL aliquot obtained BSA added (please check boxes) Sample #101	End 24-hour Collection Time:			
Date	Time	Volume of Void	Record comments (i.e., if collection missed), and sign each time you collect a sample																																																																								
Pre-Drug Administration (Sample 100)																																																																											
Administer CB-5339, Time:																																																																											

DAY 1 Start 24-hour urine collection immediately after study drug administration, keep on ice. Add 1.5% BSA to collection flask and mix well. Record volume of each void on this sheet and record total 24-hour volume at the end of the collection. At the end of 24 hours, retain 10 mL aliquot only, place on ice and discard remainder of urine.
																																																																											
Date	Time (start of 24 hr collection time)	Volume of Void	24-hour urine collection																																																																								
			Volume 1																																																																								
			Volume 2																																																																								
			Volume 3																																																																								
			Volume 4																																																																								
			Volume 5																																																																								
			Volume 6																																																																								
			Volume 7																																																																								
			Volume 8																																																																								
			Volume 9																																																																								
			Volume 10																																																																								
Total (24-hour volume)			10 mL aliquot obtained BSA added (please check boxes) Sample #101																																																																								
End 24-hour Collection Time:																																																																											

SAMPLE COLLECTION SHEET: Cycle 1 Day 1 and Day 2 (escalation phase)				All patients	
CTEP Protocol 10349 CB-5339 Dose: Patient ID: PK SAMPLES GO ON ICE		Ht: Wt: BSA:	Page [name] for Sample Pick-up Lab [contact]		Research Nurse: Phone: PI: [name] [contact]
PLEASE LABEL EACH TUBE WITH ACTUAL DATE AND TIME OF SAMPLE COLLECTION					
Day	Time	Instructions	Ideal Time	Actual Time	Record comments (i.e., if collection missed), and sign each time you collect a sample
Day 1	Prior to drug administration	PK 200 1 x 0.5mL K ₂ EDTA Label tube: sample number, date and time			
Day 1	Prior to drug administration	PD 300 1x 6-mL NaHep Label tube: sample number, date and time			
Administer CB-5339: Time: _____					
Day 1	15 mins after administration	PK 201 1 x 0.5mL K ₂ EDTA Label tube: sample number, date and time			
Day 1	30 mins after administration	PK 202 1 x 0.5mL K ₂ EDTA Label tube: sample number, date and time			
Day 1	1 hr after drug administration	PK 203 1 x 0.5mL K ₂ EDTA Label tube: sample number, date and time			
Day 1	2 hr after drug administration	PK 204 1 x 0.5mL K ₂ EDTA Label tube: sample number, date and time			
Day 1	4 hr after drug administration	PK 205 1 x 0.5mL K ₂ EDTA Label tube: sample number, date and time			
Day 1	4-6 hr after administration	PD 301 1x 6-mL NaHep Label tube: sample number, date and time			
Day 1	6 hr after drug administration	PK 206 1 x 0.5mL K ₂ EDTA Label tube: sample number, date and time			
Day 1	8 hr after drug administration	PK 207 1 x 0.5mL K ₂ EDTA Label tube: sample number, date and time			Sample optional
Day 2	24 hr after D1 administration	PK 208 1 x 0.5mL K ₂ EDTA Label tube: sample number, date and time			
Day 2	24 hr after D1 administration	PD 302 1x 6-mL NaHep Label tube: sample number, date and time			

Date:		SAMPLE COLLECTION SHEET: Cycle 1 Day 4 and Day 5 (escalation phase) patients 1-3 only				
CTEP Protocol 10349 CB-5339 Dose: Patient ID: PK SAMPLES GO ON ICE		Ht: Wt: BSA:	Page [name] for Sample Pick-up Lab [contact]		Research Nurse: Phone: PI: [name]	
[contact]						
PLEASE LABEL EACH TUBE WITH ACTUAL DATE AND TIME OF SAMPLE COLLECTION						
Day	Time	Instructions	Ideal Time	Actual Time	Record comments (i.e., if collection missed), and sign each time you collect a sample	
Day 4	Prior to drug administration	PK 209 1 x 0.5mL K ₂ EDTA Label tube: sample number, date and time				
Administer CB-5339: Time: _____						
Day 4	15 mins after administration	PK 210 1 x 0.5mL K ₂ EDTA Label tube: sample number, date and time				
Day 4	30 mins after administration	PK 211 1 x 0.5mL K ₂ EDTA Label tube: sample number, date and time				
Day 4	1 hr after drug administration	PK 212 1 x 0.5mL K ₂ EDTA Label tube: sample number, date and time				
Day 4	2 hr after drug administration	PK 213 1 x 0.5mL K ₂ EDTA Label tube: sample number, date and time				
Day 4	4 hr after drug administration	PK 214 1 x 0.5mL K ₂ EDTA Label tube: sample number, date and time				
Day 4	6 hr after drug administration	PK 215 1 x 0.5mL K ₂ EDTA Label tube: sample number, date and time				
Day 4	8 hr after drug administration	PK 216 1 x 0.5mL K ₂ EDTA Label tube: sample number, date and time			Sample optional	
Day 5	24 hr after D1 administration	PK 217 1 x 0.5mL K ₂ EDTA Label tube: sample number, date and time				

SAMPLE COLLECTION SHEET: PATIENTS WHO HAVE BEEN DOSE-ADJUSTED (OPTIONAL)					
CTEP Protocol 10349 CB-5339 Dose: Patient ID: PK SAMPLES GO ON ICE		Ht: Wt: BSA:	Page [name] for Sample Pick-up Lab [contact]		Research Nurse: Phone: PI: [name] [contact]
PLEASE LABEL EACH TUBE WITH ACTUAL DATE AND TIME OF SAMPLE COLLECTION					
Day	Time	Instructions	Ideal Time	Actual Time	Record comments (i.e., if collection missed), and sign each time you collect a sample
Day 1	Prior to drug administration	PK 20X 1 x 0.5mL K ₂ EDTA Label tube: sample number, date and time			
Administer CB-5339: Time: _____					
Day 1	1 hr after administration	PK 20X 1 x 0.5mL K ₂ EDTA Label tube: sample number, date and time			
Day 1	2 hr after administration	PK 20X 1 x 0.5mL K ₂ EDTA Label tube: sample number, date and time			
Day 2	24 hr after D1 administration	PK 20X 1 x 0.5mL K ₂ EDTA Label tube: sample number, date and time	Prior to D2 dose		

SAMPLE COLLECTION SHEET: Cycle 1 Day 1 (expansion phase)					
CTEP Protocol 10349 CB-5339 Dose: Patient ID: PK SAMPLES GO ON ICE			Ht: Wt: BSA:	Page [name] for Sample Pick-up Lab [contact]	Research Nurse: Phone: PI: [name] [contact]
PLEASE LABEL EACH TUBE WITH ACTUAL DATE AND TIME OF SAMPLE COLLECTION					
Day	Time	Instructions	Ideal Time	Actual Time	Record comments (i.e., if collection missed), and sign each time you collect a sample
Day 1	Prior to drug administration	PD 800 1x 10-mL Streck Label tube: sample number, date and time			
Day 1	Prior to drug administration	PK 200 1 x 0.5mL K ₂ EDTA Label tube: sample number, date and time			
Day 1	Prior to drug administration	PD 300 1x 6-mL NaHep Label tube: sample number, date and time			
Administer CB-5339: Time: _____					
Day 1	15 min after administration	PK 201 1 x 0.5mL K ₂ EDTA Label tube: sample number, date and time			
Day 1	30 min after administration	PK 202 1 x 0.5mL K ₂ EDTA Label tube: sample number, date and time			
Day 1	1 hr after drug administration	PK 203 1 x 0.5mL K ₂ EDTA Label tube: sample number, date and time			
Day 1	2 hr after drug administration	PK 204 1 x 0.5mL K ₂ EDTA Label tube: sample number, date and time			
Day 1	4 hr after drug administration	PK 205 1 x 0.5mL K ₂ EDTA Label tube: sample number, date and time			
Day 1	4-6 hr after administration	PD 301 1x 6-mL NaHep Label tube: sample number, date and time			
Day 1	6 hr after drug administration	PK 206 1 x 0.5mL K ₂ EDTA Label tube: sample number, date and time			
Day 1	8 hr after drug administration	PK 207 1 x 0.5mL K ₂ EDTA Label tube: sample number, date and time	Optional		
Day 2	24 hr after D1 administration	PK 208 1 x 0.5mL K ₂ EDTA Label tube: sample number, date and time	Prior to D2 drug		
Day 2	24 hr after D1 administration	PD 801 1x 10-mL Streck Label tube: sample number, date and time	Prior to D2 drug		

Expansion phase

SAMPLE COLLECTION SHEET: Cycle 3 and onwards (expansion phase)						
CTEP Protocol 10349 CB-5339 Dose: Patient ID: PK SAMPLES GO ON ICE			Ht: Wt: BSA:	Page [name] for Sample Pick-up Lab [contact]		Research Nurse: Phone: PI: [name] [contact]
PLEASE LABEL EACH TUBE WITH ACTUAL DATE AND TIME OF SAMPLE COLLECTION						
Day	Time	Instructions	Ideal Time	Actual Time	Record comments (i.e., if collection missed), and sign each time you collect a sample	
Day 1	Prior to drug administration	PD 80X 1x 10-mL Streck Label tube: sample number, date and time				
Administer CB-5339: Time: _____						

SAMPLE COLLECTION SHEET: Day of restaging follow-up or progression biopsy per PI						
CTEP Protocol 10349 CB-5339 Dose: Patient ID: PK SAMPLES GO ON ICE			Ht: Wt: BSA:	Page [name] for Sample Pick-up Lab [contact]		Research Nurse: Phone: PI: [name] [contact]
PLEASE LABEL EACH TUBE WITH ACTUAL DATE AND TIME OF SAMPLE COLLECTION						
Day	Time	Instructions	Ideal Time	Actual Time	Record comments (i.e., if collection missed), and sign each time you collect a sample	
Day	Prior to drug administration	PD 80X 1x 10-mL Streck Label tube: sample number, date and time				
Administer CB-5339 if appropriate: Time: _____						

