7. BIOMARKER AND CORRELATIVE STUDIES

Blood and urine will be obtained from all patients to determine the PK of CB-5339; BSA additive should be included in the urine collection flask per Section 7.1. Pre- and post-treatment tumor biopsies will be collected on the expansion cohort to measure the effects of CB-5339 on the ubiquitin proteasome system and on markers of cell death; PBMCs will be collected on the escalation cohort as surrogate markers for tumor effect. Blood samples will also be collected for isolation of circulating tumor DNA (ctDNA) as an exploratory endpoint to identify potential genomic biomarkers of response in patients on the expansion cohort.

Record the date, planned time and actual time of collection for each specimen on the PK/PD sample collection sheet

Ophthalmologic Examination will be performed at screening and as clinically indicated.

Ophthalmologic testing and biomicroscopic examinations should include assessment of the following in the order listed whenever possible.

- Best corrected visual acuity (BCVA) using Early Treatment Diabetic Retinopathy Study (ETDRS) methodology. The same methodology is to be used for the pre-study and follow-up examinations for each individual subject.
- Slit lamp examination including assessment of the lids, lashes, conjunctiva, sclera, cornea, anterior chamber, iris, lens and anterior vitreous. The slit lamp examination is repeated following dilation to better assess the lens and anterior vitreous.
- Measurement of intra-ocular pressure.
- Fundus examination. This include assessment of the vitreous, retina, disc, macula, vessels, and periphery of each eye using dilated fundoscopy.
- Spectral domain optical coherence tomography (OCT) of the macula and disc for both eyes. The same type of device is to be used for the pre-study and follow-up examinations for each individual subject.
- Standard field fundus photographs with the pupils dilated performed on each eye to aid in the evaluation of the optic nerve, vessels, macula, and periphery.
- Color vision testing

To be eligible for this research protocol, patients will be screened for pre-existing visual impairment. Patients will be excluded if they do not meet the visual acuity threshold (best corrected visual acuity of 60 ETDRS letters [Snellen equivalent of 20/60] in either eye) and the visual field threshold (substantial visual field loss in one or both eyes).

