7.2.5 Blood Collection for Peripheral Blood Mononuclear Cells (PBMCs)

Whole blood will be collected aseptically by venipuncture or from a venous port into one 6 mL NaHep tube and the cells pelleted per SOP (Appendix E).

PBMC collection will be mandatory during both the dose escalation and expansion phases:

- cycle 1 prior to CB-5339 administration
- cycle 1 day 1, 4-6 hrs after drug administration
- One additional blood sample (optional) may be collected at/near time of disease progression.

Samples will be sent for K-48 ubiquitin linked protein and CHOP measurements in the laboratory of [name], NCI-Frederick.

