7.2.6 Blood Collection for exploratory ctDNA Studies

Whole blood (7.5 mL per collection) will be collected aseptically by venipuncture or from a venous port into one 10-mL Streck cell-free DNA tube. Blood samples for should be shipped as soon as possible so they can be analyzed within 48 hours of collection (preferably, within 24 hours of collection).

Blood samples for ctDNA will be optional during the dose escalation phase, mandatory during the expansion cohort:

- cycle 1 prior to CB-5339 administration
- cycle 1 day 2 (at any time)
- day 1 of every subsequent cycle (at any time)
- One additional blood sample (optional) may be collected at/near time of disease progression.

Testing and data analysis will be performed by MoCha on the Illumina TSO 500 panel of oncology-related genes (non-CLIA).

Ship ctDNA blood specimens at ambient temperature to:

Attn: [name]/[name]
Molecular Characterization Lab
Frederick National Laboratory for Cancer Research
[name]
[name]
[name]
[contact] or [contact]
[contact]

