7.3 Biomarker Plan

List of Biomarker Assays in order of priority use

Priority	Biomarker Name	Assay CLIA?	Use in the Trial and Purpose	Specimens Tested	Collection Time Points	Mandatory or Optional	Assay Laboratory and Lab PI
Biomarkers and correlative studies							
1	Cytosolic K48 ubiquitination	Luminex-based multiplexed sandwich immunoassay for K48 ubiquitination, nuclear CHOP, and cytoplasmic cleaved caspase-3 CLIA: No	Integrated Proof-of-mechanism (measurement of proteasome pathway blockage by assessing the build-up of K48-ubiquitinated proteins in the cytosol)	Tumor biopsy tissue PBMCs	Baseline and cycle 1, day 1, 4-6 hours after treatment (optional at disease progression)	Tumors mandatory for the expansion cohort only (progression biopsy always optional) PBMCs mandatory both	PADIS: [name] [contact]
2	Nuclear CHOP	Luminex-based multiplexed sandwich immunoassay for K48 ubiquitination, nuclear CHOP, and cytoplasmic cleaved caspase-3 CLIA: No	Exploratory Proof-of-mechanism (measurement of the unfolded protein response by assessing the induction of the transcription factor CHOP in the nucleus)	Tumor biopsy tissue PBMCs	Baseline and cycle 1, day 1, 4-6 hours after treatment (optional at disease progression)	Tumors mandatory for the expansion cohort only (progression biopsy always optional) PBMCs mandatory both	PADIS: [name] [contact]
3	Cytosolic Cleaved Caspase-3	Luminex-based multiplexed sandwich immunoassay for K48 ubiquitination, nuclear CHOP, and cytoplasmic cleaved caspase-3 CLIA: No	Exploratory To identify biomarkers of response (measurement of the execution of apoptosis by the accumulation of cleaved caspase-3 in the cytosol)	Tumor biopsy tissue PBMCs	Baseline and cycle 1, day 1, 4-6 hours after treatment (optional at disease progression)	Tumor mandatory for the expansion cohort only (progression biopsy always optional) PBMCs mandatory both	PADIS: [name] [contact]

Priority	Biomarker Name	Assay CLIA?	Use in the Trial and Purpose	Specimens Tested	Collection Time Points	Mandatory or Optional	Assay Laboratory and Lab PI
Biomarkers and correlative studies							

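### The Appendix C worksheets skip the mandatory cycle 2 ctDNA sample in expansion and add a 24-hour PBMC tube in escalation that Section 7 does not list

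*Combined protocol and SAP*

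**What the plan says.** **ctDNA.** Section 7.2.6 makes ctDNA blood optional in escalation and mandatory in expansion. The time points are cycle 1 pre-dose, cycle 1 day 2, and then "day 1 of every subsequent cycle (at any time". The Section 7.3 table also calls for a sample at each cycle start, and the study calendar (Section 10) marks ctDNA at cycle 2 week 1. In Appendix C, the expansion sheet for cycle 1 carries Streck tubes PD 800 and PD 801. The next expansion sheet is "SAMPLE COLLECTION SHEET: Cycle 3 and onwards (expansion phase".

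**PBMCs.** Section 7.2.5 states "PBMC collection will be mandatory during both the dose escalation and expansion phases". It lists a cycle 1 pre-dose sample, one at "cycle 1 day 1, 4-6 hrs after drug administration", and an optional one: "One additional blood sample (optional) may be collected at/near time of disease progression". Section 7.3 gives the same plan: "Baseline and cycle 1, day 1, 4-6 hours after treatment (optional at disease progression". The schema agrees. The escalation worksheet for cycle 1 days 1 and 2, marked as applying to all patients, carries PD 300, PD 301 and, on Day 2 at 24 hours, "PD 302 1x 6-mL NaHep Label tube: sample number, date and time". The expansion worksheet stops at PD 301.

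**Role of the sheets.** Section 7 tells staff to record planned and actual collection times on the collection sheet. Section 7.2.8 says specimen information goes on the Appendix C worksheet.

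**The concern.** The worksheet is what staff have in hand on the day. A tube with no line on it is easily missed, and a line with no basis in the schedule still prompts a draw. Here staff cannot satisfy both Section 7 and Appendix C.

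PBMC pharmacodynamics is part of a secondary objective (Section 1.2), and ctDNA serves the exploratory objective (Section 1.3). A cycle 2 sample not taken on the day cannot be recovered. A 24-hour PBMC value collected in one phase and not the other cannot be pooled or compared across phases. The extra tube is also blood drawn from patients that the visible schedules do not call for.

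**Working it through.** The plan gives no figure to reproduce, so the check is a tally of tubes by phase and time, Section 7 against Appendix C.

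| Sample | Section 7, schema, calendar | Appendix C |
|---|---|---|
| Escalation PBMC, cycle 1 | 2 (pre-dose, 4-6 h) | 3 (adds PD 302 at 24 h) |
| Expansion PBMC, cycle 1 | 2 | 2 |
| Expansion ctDNA, cycle 2 day 1 | 1, mandatory | 0 |
| PBMC at progression | 1, optional | 0 |

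**PD 302 is a PBMC tube.** Section 7.2.5 names a 6 mL NaHep tube for PBMCs, and Section 7.2.8 assigns the 300 series to PD blood. The row is not marked optional, although the 8-hour PK row on the same sheet is. On the expansion sheet the Day 2 rows are PK 208 and a Streck tube (PD 801), with no NaHep tube.

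**ctDNA gap.** Cycles last 28 days (Section 5.1).
- Cycle 2 day 1 = 28 + 1 = day 29.
- Cycle 3 day 1 = 2 × 28 + 1 = day 57.
- Section 7.2.6 gives days 1, 2, 29, 57; the longest gap is 57 − 29 = 28 days.
- The sheets give days 1, 2, 57; the gap is 57 − 2 = 55 days.
- Samples at risk: 15 expansion patients × 1 = 15 at most.

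**Extra PBMC blood.**
- Scheduled on cycle 1 days 1-2: 2 × 6 mL = 12 mL. On the escalation sheet: 3 × 6 mL = 18 mL. Excess: 6 mL per patient.
- With 6-18 escalation patients planned (Section 8.2), that is 6 to 18 unlisted tubes.

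**Time points at the RP2D.** Section 5.2 requires at least 6 patients at the RP2D, and Section 5.3 adds 15. Taking 6 as the escalation number, 6 + 15 = 21 patients would have pre-dose and 4-6 hour PBMCs there. Only the 6 who used the escalation sheet would also have a 24-hour value.

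**Two smaller slips.** The restaging/progression sheet has a Streck tube only, so the optional progression PBMC has no line. The Day 5 row for patients 1-3 (PK 217) is described as 24 hours after the Day 1 dose, whereas Section 7.1 places it 24 hours after the Day 4 dose.

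**The case against.** The best defence is that the body of the protocol governs and is consistent. Sections 7.2.6 and 7.3, the schema and the calendar all require ctDNA at each cycle start, so attentive staff would take the cycle 2 sample anyway. ctDNA is exploratory, and no longitudinal ctDNA analysis is specified (Section 8.3.2). This is fair: it makes 15 an upper bound and keeps the matter minor. It does not explain a mandatory sample with no worksheet line, or an extra tube with no listing.

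A reader might infer more than the documents support:
- *That the 24-hour PBMC point would be missing at the RP2D.* At least 6 patients are entered there under Section 5.2, apart from the 15 added in expansion, and the escalation sheet gives them PD 302.
- *That it would be lost where it could be paired with tumor tissue.* The scheduled on-treatment biopsy is at 4-6 hours (Section 7.2.1), so no time-matched tumor sample exists at 24 hours in either phase.
- *That PK 217 would be analysed at 96 hours.* Day 5 is indeed 96 hours after the Day 1 dose, but the label says 24 hours. The sheet is headed for Days 4 and 5, has its own dose-time line and requires actual date and time on each tube. It is a labelling slip.
- *That Section 7's opening contradicts Section 7.2.5.* It says "PBMCs will be collected on the escalation cohort as surrogate markers for tumor effect", which gives their role where no biopsy is scheduled and does not confine them to escalation.
- *That no progression PBMC could be collected.* A missing line for an optional sample is not a prohibition.

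**Conclusion.** The point holds as a minor internal inconsistency with two parts that affect which samples are collected. First, no expansion sheet prompts the mandatory cycle 2 day 1 ctDNA sample. Up to 15 exploratory samples are at risk, fewer if patients stop before cycle 2 or staff follow Section 7. Second, the escalation sheet draws an unlisted 6 mL PBMC tube at 24 hours from each of the 6-18 planned escalation patients. PBMC time points would therefore differ between escalation and expansion.

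The primary endpoint, DLT rules and sample size are unaffected. So is the PD power in Section 8.3, which rests on paired tumor biopsies.

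Two assumptions apply. A stray line about the expansion phase stands before the cycle 3 sheet, so a cycle 2 sheet lost when the PDF was read cannot be wholly excluded, although nothing marks a gap there. Section 7.2.7 was not in the text available; the three visible PBMC schedules agree that there is no 24-hour draw.

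**What to change.** 1. Retitle the later-cycle expansion sheet *Cycle 2 and onwards (expansion phase)*.
2. Delete PD 302 from the escalation sheet so that it matches Sections 7.2.5 and 7.3. If the sponsor wants the 24-hour point, list it in Section 7.2.5, Section 7.3 and the schema, and add it to the expansion sheet.
3. In the same amendment, add an optional 6 mL NaHep line to the restaging/progression sheet and relabel PK 217 *24 hr after D4 administration*.

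The cost is worksheet edits in an amendment. Deleting PD 302 reduces the blood drawn. Keeping it also needs the schedule text changed and adds one draw for up to 15 expansion patients, so that choice should be deliberate.
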